5.5. Tertiary/Exploratory Endpoint(s) Analysis

No tertiary and exploratory analyses are planned in this study.

5.6. Safety Analyses

Safety data will be summarized descriptively. No formal statistical testing of safety data is planned. If analysis by age group and by history of UTI is performed, stratification factor data are obtained as collected from the eCRF.

Safety endpoints (secondary endpoints):

- Solicited local (in each injection site for the first vaccination) and systemic AEs for 14 days post each vaccination
- Unsolicited AEs for 29 days post each vaccination
- MAAEs and SAEs collected from the administration of first vaccination until 6 months post last vaccination

Safety analyses will be performed on the FAS. Continuous variables will be summarized using the following statistics, as appropriate: number of observations, mean, 95% CI for the mean, median, quartiles (1st and 3rd), minimum, and maximum. Frequencies and percentages (one decimal place) will be generated for categorical variables. No formal comparisons between groups will be provided.

Safety data will be analyzed and presented by study intervention and phase, and across the entire study period where applicable. For solicited AEs, the denominator for the percentages is the number of participants with data assessed by the investigator in the considered population and phase for a certain regimen (incidence per 100 participants/phase). For unsolicited AE, the denominator for the percentages is the number of participants in the considered population and phase for a certain regimen (incidence per 100 participants/phase).

5.6.1. Adverse Events

5.6.1.1. Definitions

Solicited AEs shown in the tables are extracted from the investigator assessment pages (Clinical Events) of the eCRF. All solicited AEs at the injection site (local) are considered related to the study vaccine administration.

For unsolicited AEs, only the AEs within the 29-day period following each vaccination will be presented in the safety tables except for MAAE and SAE which will be captured and tabulated in the outputs covering the whole study period.

The severity of the AEs will be classified as Grade 1 to 4. Solicited or unsolicited events that are graded less than Grade 1, are not considered as AE.

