**Table 1: Overview of the Groups, Targeted Number of Participants, and Vaccinations**

Group	N	Day 1	Day 30
1 (CoAd group)	~466	ExPEC9V + HD quadrivalent seasonal influenza vaccine	Placebo
2 (Control group)	~466	Placebo + HD quadrivalent seasonal influenza vaccine	ExPEC9V

N = number of participants.

After each vaccination, participants will be observed for at least 30 minutes for presence of any acute reactions and solicited events. Any unsolicited AEs, solicited local (injection site) or systemic AEs, and vital signs (systolic and diastolic blood pressure [sitting], heart rate, respiratory rate, and body temperature) will be documented by study-site personnel following this observation period. In addition, participants will record solicited signs and symptoms in an eDiary for 14 days post-vaccination.

Unsolicited AEs will be reported for 29 days post-vaccination. SAEs, MAAEs, and AEs leading to discontinuation from the study/vaccination (regardless of the causal relationship) are to be reported from the moment of first vaccination until completion of the participant's last study-related procedure. More details are provided in Section 8.3.1., Time Period and Frequency for Collecting Adverse Event and Serious Adverse Event Information.

The study duration will be approximately 7 months per participant. The study comprises screening to be performed within 8 days of Day 1, vaccination for each participant on Days 1 and 30 with a 29-day follow-up period after each vaccination, and collection of SAEs and MAAEs until 6 months after the last study vaccination.

Unscheduled study visits may be performed based on investigator's clinical judgment and may include further evaluations, as needed.

Blood will be collected from all participants to assess humoral immune responses on each vaccination day (prevaccination) and at 29 days after the second study vaccination. Over the entire study, the total blood volume to be collected from each participant will be approximately 90 mL.

A diagram of the study design is provided in Section 1.2, Schema (Figure 1).

An IDMC will be commissioned for this study. Refer to Committees Structure in Section 10.2, [Appendix 2: Regulatory, Ethical, and Study Oversight Considerations](#) for details.

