#### **Serious Adverse Events and Adverse Events Leading to Discontinuation**

All SAEs and AEs leading to discontinuation from the study/vaccination are to be reported from the moment of first vaccination until completion of the participant's last study-related procedure, which may include contact for safety follow-up. The sponsor will evaluate any safety information that is spontaneously reported by an investigator beyond the time frame specified in the protocol.

All SAEs occurring during the study must be reported to the appropriate sponsor contact person by study-site personnel immediately, but no later than 24 hours of their knowledge of the event.

Information regarding SAEs will be transmitted to the sponsor using the Serious Adverse Event Form and Safety Report Form of the eCRF, which must be completed and reviewed by a physician from the study site, and transmitted to the sponsor immediately but no later than within 24 hours. The initial and follow-up reports of an SAE should be transmitted electronically or by facsimile (fax).

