5.6.1.2. Analysis of Adverse Events

The verbatim terms used in the eCRF by investigators to identify AEs will be coded using the Medical Dictionary for Regulatory Activities.

Number and percentage of participants with at least one specific AE (solicited/unsolicited) will be tabulated. Solicited AEs will be summarized by class (local and systemic) and preferred term. Unsolicited AEs will be summarized by System Organ Class and Preferred Term.

For solicited AEs, following tables will be provided: summary, by worst severity grade, at least Grade 3, related (systemic only), time to onset (in days) and duration (in days). Note: Duration is defined as number of days from the start of the event until resolution of the event. The time to first onset is defined as (date of first onset – reference date + 1). The reference date is the start date of the vaccination period.

For unsolicited AEs, the following tables will be provided as appropriate: summary, all events, most frequent, at least Grade 3, related AE, AE leading to study vaccine discontinuation, AE leading to study discontinuation, participants who died, MAAE, related MAAE, SAE and related SAE.

Summaries, listings, datasets, or participant narratives may be provided, as appropriate, for those participants who die, who discontinue vaccination due to an AE, who discontinue study due to an AE, MAAE or who experience a severe or a SAE.

Summaries and/or listings may be provided separately for AEs with onset outside the above defined timeframe (i.e., beyond 29 days post-vaccination).

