5.8. Interim Analyses

No formal interim analysis is planned for this study.

The primary analysis will take place when all participants have performed their Day 59 visit or are discontinued earlier. The primary analysis will include all available safety data and immunogenicity results up to Day 59. The analysis will be performed based on sponsor unblinded data.

The final analysis will include MAAE and SAE data up to the end of the study and will be performed on unblinded data.

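### The SAP's 29-day table limit exempts MAAEs and SAEs but not AEs leading to discontinuation, so the study-discontinuation table can miss late, non-serious, non-medically-attended events

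*SAP*

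**What the plan says.** - **Table limit.** SAP Section 5.6.1.1, on unsolicited AEs: "only the AEs within the 29-day period following each vaccination will be presented in the safety tables except for MAAE and SAE". The two exempt classes are those "which will be captured and tabulated in the outputs covering the whole study period".
- **Planned tables.** SAP Section 5.6.1.2 lists, under unsolicited AEs, "AE leading to study vaccine discontinuation, AE leading to study discontinuation", and gives these two tables no window of their own. The same section permits, but does not require, separate output for AEs starting beyond 29 days and summaries, listings or narratives for participants who stop because of an AE.
- **Final analysis.** SAP Section 5.8: "The final analysis will include MAAE and SAE data up to the end of the study". AEs leading to discontinuation are not mentioned. The matching sentence in Protocol Section 9.5 names SAE data only.
- **Collection.** Protocol Section 8.3.1: "All SAEs and AEs leading to discontinuation from the study/vaccination are to be reported from the moment of first vaccination until completion"; the end point meant there is the final study procedure for that participant. Protocol Section 4.1 groups all three classes together: "SAEs, MAAEs, and AEs leading to discontinuation from the study/vaccination (regardless of the causal relationship) are to be reported" over that period. Other unsolicited AEs are collected only for 29 days after each vaccination.
- **Disposition.** SAP Section 5.2 counts study discontinuations, missed second vaccinations and the reasons for each throughout the study.

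**The concern.** The protocol gave AEs leading to discontinuation the long collection period, and the SAP plans tables under that name. The rule that decides which events enter the safety tables nevertheless treats them like ordinary unsolicited AEs and stops 29 days after each vaccination. Events that sites must report then have no assured place in the table meant for them.

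Two things are at stake. The AE study-discontinuation table can err only towards too few events. It may also disagree with the disposition table, which counts reasons for leaving over the whole study, and a reader of the study report would have no stated explanation for the difference.

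**Working it through.** The plan states no figure on this point, so there is nothing to reproduce. The check sets the rules side by side and then counts days.

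**1. Rules compared**

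| Event class | Collected until (Protocol 4.1, 8.3.1) | Exempt from 29-day limit (SAP 5.6.1.1) | Named for final analysis (SAP 5.8) |
|---|---|---|---|
| SAEs | last study procedure | yes | yes |
| MAAEs | last study procedure | yes | yes |
| AEs leading to discontinuation | last study procedure | no | no |
| Other unsolicited AEs | 29 days after each vaccination | no | no |

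The third row is the only one in which collection and tabulation disagree.

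**2. Inputs for the day count**

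- Vaccinations on Days 1 and 30; last visit on Day 210, window ±42 days (Protocol Section 1.3).
- Visits 3 and 5 (Days 30 and 59) each have a ±7-day window (Protocol Section 1.3).
- Dose 2 may be delayed by up to 10 days beyond the Visit 3 window (Protocol Section 5.5).

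**3. Study discontinuation, both doses given on schedule**

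- First window ends: 1 + 29 = Day 30. Second window ends: 30 + 29 = Day 59.
- Uncovered: Days 60 to 210, or 210 − 59 = 151 days. This is 151/209 = 72% of the days after Day 1, and 151/180 = 84% of the days after dose 2.
- Across the ±42-day window of the last visit: 168 − 59 = 109 to 252 − 59 = 193 days.
- If the limit follows the Post-dose 2 period in SAP Table 4, which runs to the completed visit when that is later, coverage could reach 59 + 7 = Day 66. The uncovered part is then 210 − 66 = 144 days.

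**4. Study discontinuation, dose 2 not given**

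- Uncovered from Day 31: 210 − 30 = 180 days, 180/209 = 86%.
- If SAP Table 4 applies and Visit 3 takes place at +7 days, uncovered from Day 38: 210 − 37 = 173 days.

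**5. Vaccination discontinuation**

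Only dose 2 can be discontinued, and an AE that stops it will normally start within 29 days of dose 1. The exception is a new AE that arises while dose 2 is being delayed.

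- Latest permitted dose 2: 30 + 7 + 10 = Day 47.
- Largest gap: Days 31 to 46, or 16 days. With the Table 4 period end at Day 37, it shrinks to Days 38 to 46, or 9 days.

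**6. Which events are certain to be lost**

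A late event that is also serious or medically attended must appear in the whole-study SAE or MAAE output. The sure loss is therefore late, non-serious, non-medically-attended AEs that lead to discontinuation. As a hypothetical case, a participant develops a troublesome symptom on Day 120, sees no clinician and leaves the study because of it. The event is reportable and the departure is counted in disposition, but the AE is outside the study-discontinuation table.

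**The case against.** The strongest case against is that the affected class is very small. The MAAE definition in Protocol Section 8.3.1 is broad, taking in visits to or from medical personnel for any reason, so few AEs that make someone leave a study would escape it. After Day 59 the only scheduled contact is a telephone call, with no vaccination or blood draw, so there is little to withdraw from. The withdrawal reasons in Protocol Section 7.2 do not list an AE, and participants stopped from further vaccination are meant to stay in follow-up. The SAP rule also matches the declared safety endpoints, in which AEs leading to discontinuation do not appear, and the treatment-emergent window in Protocol Section 9.4.4. All of this stands, and it limits the importance of the point.

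It can also be said that the SAP already provides for such events through optional output for late AEs, optional narratives, and presentation over the entire study where applicable (Section 5.6). This stands only in part. Optional output does not complete a planned table, and a general phrase does not override the specific sentence that limits the tables.

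A reader might infer four stronger things that the documents do not support:

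- *That the loss begins at Day 29 or 30 for everyone.* The limit runs from each vaccination, so with dose 2 on Day 30 onsets up to Day 59 are tabulated.
- *That late SAEs and MAAEs causing discontinuation are kept out of the discontinuation tables.* The SAP sends them to whole-study outputs and does not say whether they also enter the discontinuation tables.
- *That the gap hides poor tolerability of ExPEC9V in the Control group.* Control participants waiting for a delayed dose 2 have not yet received ExPEC9V.
- *That these discontinuations vanish from the report.* Disposition still counts them and their reasons.

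**Conclusion.** The omission is real and minor. Followed as written, the SAP gives no assured whole-study table for a class of AEs that the protocol collects to the end of the study. The main exposure is the study-discontinuation table: Days 60 to 210 on the nominal schedule, or from about Day 31 when dose 2 is not given. The vaccine-discontinuation table has a gap of at most 16 days, and only for a new AE during a permitted delay.

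These are lengths of calendar time, not numbers of events. The documents give no rate from which a count could be derived. That the count is probably small is a judgement from the breadth of the MAAE definition and the telephone-only follow-up. The day counts assume the nominal schedule and a literal reading of the 29-day limit; the period ends in SAP Table 4 would shorten each gap by up to 7 days. No endpoint, hypothesis or primary conclusion is affected. The consequence is an incomplete table that may not reconcile with disposition.

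**What to change.** - **SAP Section 5.6.1.1:** extend the exemption to three classes, namely MAAEs, SAEs, and AEs leading to discontinuation of study or vaccination, all tabulated over the whole study period.
- **Same section:** state that late-onset MAAEs and SAEs that lead to discontinuation also enter the discontinuation tables, so that those tables can be reconciled with the disposition reasons.
- **SAP Section 5.8:** add AEs leading to discontinuation to the final-analysis sentence. Align Protocol Section 9.5, which at present names SAEs only.

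The cost is a phrase or sentence in each place and a changed table filter. The protocol already requires these data to be collected, so no new data are needed.

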**Solicited Adverse Events**

Solicited AEs are used to assess the reactogenicity of the study vaccine and are predefined local (at injection site) and systemic events for which the participant is specifically questioned and which are noted by participants in their eDiary.

After each vaccination, participants will be observed for at least 30 minutes for presence of any acute reactions and solicited events.

In addition, participants will record solicited signs and symptoms in an eDiary for 14 days post-vaccination. All participants will be provided with an eDiary and instructions on how to complete the eDiary (see Overview in Section 8., Study Assessments and Procedures). Electronic diary information will be transferred from the eDiary source to the sponsor. Review of eDiary entries with participants and grading of symptoms must be done by a qualified and delegated study staff member under the oversight of the investigator or a delegated physician. Once a solicited sign or symptom from an eDiary is considered to be of severity Grade 1 or above, it will be recorded as a solicited AE.

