##### **Adverse Event**

An AE is any untoward medical occurrence in a clinical study participant administered a pharmaceutical (investigational or non-investigational) product. An AE does not necessarily have a causal relationship with the study vaccination. An AE can therefore be any unfavorable and unintended sign (including an abnormal finding), symptom, or disease temporally associated with the use of a medicinal (investigational or non-investigational) product, whether or not related to that medicinal (investigational or non-investigational) product. (Definition per International Council on Harmonisation [ICH])

This includes any occurrence that is new in onset or aggravated in severity or frequency from the baseline condition, or abnormal results of diagnostic procedures, including laboratory test abnormalities.

Note: For the time period of the sponsor's AE collection, see All Adverse Events under Section 8.3.1., Time Period and Frequency for Collecting Adverse Event and Serious Adverse Event Information.

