## **10.3.3. Severity Criteria**

All AEs and laboratory data will be coded for severity using a modified version of the FDA grading table, based on version of September 2007 ([US Dept Health 2007a](#)), included in [Appendix 5: Toxicity Grading Scale](#).

For AEs/MAAEs not identified in the grading table, the following guidelines will be applied:

Grade 1	Mild	Symptoms causing no or minimal interference with usual social and functional activities
Grade 2	Moderate	Symptoms causing greater than minimal interference with usual social and functional activities
Grade 3	Severe	Symptoms causing inability to perform usual social and functional activities and requires medical intervention
Grade 4	Potentially life-threatening	Symptoms causing inability to perform basic self-care functions OR medical or operative intervention indicated to prevent permanent impairment, persistent disability OR ER visit or hospitalization

The severity of solicited signs and symptoms will be graded in the eDiary by the participant based on the severity assessment provided in the eDiary and then verified by the investigator using the toxicity grading scale in [Appendix 5: Toxicity Grading Scale](#). (Note: severity of the measured events will be derived from the diameter [for erythema and swelling] and the temperature measurements [for fever]).

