#### 10.3.5. Procedures

##### All Adverse Events

All AEs and MAAEs, regardless of seriousness, severity, or presumed relationship to study vaccine, must be recorded using medical terminology in the source document and the eCRF. Whenever possible, diagnoses should be given when signs and symptoms are due to a common etiology (eg, cough, runny nose, sneezing, sore throat, and head congestion should be reported as "upper respiratory infection"). Investigators must record in the eCRF their opinion concerning the

relationship of the AE or MAAE to study therapy. All measures required for AE and MAAE management must be recorded in the source document and reported according to sponsor instructions.

For all studies with an outpatient phase, including open-label studies, the participant must be provided with a "wallet (study) card" and instructed to carry this card with them for the duration of the study indicating the following:

- Study number
- Statement, in the local language(s), that the participant is participating in a clinical study
- Investigator's name and 24-hour contact telephone number
- Local sponsor's name and 24-hour contact telephone number (for medical personnel only)
- Site number
- Participant number
- Any other information that is required to do an emergency breaking of the blind

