5.6.2. Vital Signs

Vital signs (systolic and diastolic blood pressure [while sitting], heart rate, respiratory rate, and body temperature) will be measured both before vaccination and after the end of the 30-minute observation period. At non-vaccination visits, vital signs may be measured if deemed necessary by the investigator.

Baseline and emerging vital signs abnormalities after vaccination will be listed based on the abnormality gradings in [Appendix 4](#) (Section 6.4). An abnormality will be considered as emerging in a particular period if it is worse than the baseline value. If the baseline is missing, the abnormality is always considered emerging.

Any clinically significant changes in vital signs will be reported as an AE. Any clinically significant changes in vital signs that are observed prior to the first vaccination will be reported as medical history.

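### SAP 5.6.1.1 applies the Grade 1 floor to unsolicited events, which the protocol does not, so a reported unsolicited AE can be left out of the AE tables

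*SAP*

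**What the plan says.** SAP 5.6.1.1 gives the severity range, "The severity of the AEs will be classified as Grade 1 to 4", and then the exclusion: "Solicited or unsolicited events that are graded less than Grade 1, are not considered as AE".

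The protocol treats the two kinds of event differently.

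- **Solicited symptoms.** Protocol 8.3.2 has the Grade 1 threshold for turning a diary symptom into an AE: "Once a solicited sign or symptom from an eDiary is considered to be of severity Grade 1 or above, it will be recorded".
- **AE definition.** Protocol 10.3.1 has no severity threshold: "An AE is any untoward medical occurrence in a clinical study participant administered a pharmaceutical (investigational or non-investigational) product".
- **Recording.** Protocol 10.3.5: "All AEs and MAAEs, regardless of seriousness, severity, or presumed relationship to study vaccine, must be recorded".
- **Analysis.** Protocol 9.4.4 says that every treatment-emergent AE that is reported goes into the analysis.
- **Vital signs.** SAP 5.6.2 says: "Any clinically significant changes in vital signs will be reported as an AE". Protocol 9.4.4 has the same rule. The trigger is clinical significance, not a numeric grade.
- **Grading.** Protocol 10.3.3: "All AEs and laboratory data will be coded for severity using a modified version of the FDA grading table". Events that the table does not cover use a general four-grade scale.

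**The concern.** The SAP takes a floor that the protocol wrote for diary symptoms and extends it to unsolicited events. For a diary symptom the floor makes sense: a trace of redness should not become an AE. An unsolicited AE has already been judged worth reporting by the investigator, and the protocol says that such events are analysed.

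Unsolicited AEs and MAAEs are secondary safety endpoints. The extended floor can only take reported events out, so any error is an under-count. MAAEs are defined as AEs with a medical visit, so an event that the SAP declares not to be an AE cannot be an MAAE either. The SAP also conflicts with itself: 5.6.2 makes a clinically significant vital-sign change an AE, and 5.6.1.1 can then say that it is not one.

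**Working it through.** The plan gives no figure on this point to reproduce. The check has three parts: which events can fall below Grade 1, which cannot, and whether another output would show a removed event.

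**1. Events that can fall below Grade 1.** Only rows defined by measured values leave a range under the first cut-off. The first cut-offs are the same in Protocol Appendix 5 and SAP Appendix 4:

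| Measure | Grade 1 band | Values with no grade |
|---|---|---|
| Systolic pressure (mm Hg) | hypotension 85–89; hypertension 141–150 | 90–140 |
| Diastolic pressure (mm Hg) | hypertension 91–95 | 90 or less |
| Heart rate (per minute) | bradycardia 50–54; tachycardia 101–115 | 55–100 |
| Respiratory rate (per minute) | 17–20 | 16 or less |
| Temperature (°C) | 38.0–38.4 | below 38.0 |

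Two illustrations, with assumed values:

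- Systolic pressure falls from 150 to 92 mm Hg, a change of 150 − 92 = 58 mm Hg. It ends 3 mm Hg above the top of the hypotension Grade 1 band (92 − 89 = 3).
- Heart rate rises from 58 to 100, a change of 100 − 58 = 42 beats per minute. It ends one beat short of tachycardia Grade 1 (101).

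If the investigator judges either change clinically significant, it is an AE under SAP 5.6.2. If it is then graded strictly on its numeric row, it lies below Grade 1 and SAP 5.6.1.1 says it is not an AE.

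Laboratory rows work in the same way but matter little here, because the Schedule of Activities has no safety laboratory tests.

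**2. Events that cannot fall below Grade 1.**

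- On the general scale in Protocol 10.3.3, Grade 1 already includes symptoms that do not interfere with activities. An emergency-room visit or hospitalization is Grade 4.
- The systemic illness row in Protocol Appendix 5 also starts, at Grade 1, from an event that does not interfere with activity.
- SAP 5.6.1.4 keeps an AE with missing severity in the any-grade analysis.

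The event at risk is therefore one that has been given a numeric-row assessment below the first band. This leads to an odd result: an AE with no grade is counted, while an AE with a measured value just short of a cut-off may not be.

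**3. Whether another output would show it.** The vital-sign listing in SAP 5.6.2 is driven by the numeric grades, and SAP Appendix 4 says that this analysis uses values without clinical interpretation. A value in the right-hand column of the table has no grade, so the listing would not show it. The event could then be absent from both the AE tables and the listing.

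**The case against.** The strongest reply is that the rule may never remove anything. Neither document defines a grade below 1. Nothing says that a numeric row takes precedence over the illness row, and a pressure of 92 mm Hg can fairly be read as not covered by the hypotension row, which sends it to the general scale and to Grade 1 or higher. The values-only instruction in SAP Appendix 4 governs the vital-sign listing, not AE severity. A symptomatic fall in pressure would often be reported as a symptom or diagnosis, which can be graded at least 1. For MAAEs, the protocol excludes abnormal vital signs found at routine study visits, and SAP 5.6.1.1 says that MAAEs and SAEs are tabulated over the whole study. Safety is descriptive, and the rule is the same in both groups.

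Most of this stands, and it limits the size of the effect. It does not remove the contradiction. The SAP names unsolicited events in an exclusion rule, and the protocol says that all reported treatment-emergent AEs are analysed. The outcome depends on which row a site or programmer picks, and the documents leave that choice open. The promise to tabulate MAAEs does not help an event that the same section has declared not to be an AE.

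**Conclusion.** The SAP sentence is wrong as written, with a small expected effect. It conflicts with the protocol's recording and analysis rules and can remove a reported unsolicited AE, but only when that event is graded on a numeric row below its first cut-off. Whether this happens depends on grading practice that the documents do not settle, so the number of events cannot be estimated.

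A reader might infer that clinically significant vital-sign changes and MAAEs will drop out of the safety tables. The documents do not support that. They support only that some such events can drop out, and MAAEs are mostly outside the rule's reach for the reasons given above. Nor does anything here touch the primary non-inferiority analysis or a formal safety comparison, since none is planned.

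**What to change.** Replace the sentence in SAP 5.6.1.1 with:

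> Solicited events graded less than Grade 1 are not considered AEs. Every unsolicited AE, MAAE and SAE reported by the investigator is included in the any-grade tables whatever its grade.

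The SAP could also say that an unsolicited AE whose value is short of the Grade 1 cut-off is graded on the general scale. This is optional. It would extend the scale in Protocol 10.3.3 to events that have a named row, so it should be written as an explicit rule.

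The cost is one SAP sentence and no new data. The downside is that AE counts may be slightly higher.
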